## 5.0 Study Procedures

### 5.1 Screening and Follow-up Telephone Call

Patients attending routine dental appointments who are identified by the Investigator as meeting all the inclusion / exclusion criteria, will be approached to discuss their possible participation in the study.

If the patient and / or parent or guardian is willing for the patient to participate in the study, they will be asked to return to the dental practice for Study Visit 1, when written Informed Consent will be taken by the Investigator. Patient availability for Study Visit 2 (7 to 14 days post-imaging) will also be checked.

The Site will document all patients and / or parent or guardian provided with the Patient Information Sheet and the outcome, (whether or not recruited to the study) on a Patient Screening / Recruitment Log.

### 5.2 Study Visit 1

At this visit, written Informed Consent will be taken by the Investigator and the following information collected: –

#### Pre-Imaging Information

Demographics – date of birth, ethnicity, relevant medical history and medications.

Oral hygiene information – brushing regimen, toothpaste and any other dental products used.

#### Preparation of the Calcivis System

The Calcivis System will be prepared following the manufacturer's Instructions for Use. The Disclosing Solution should not be reconstituted more than 2 hours before the first tooth is imaged.

#### Preparation Procedures for Teeth

Relevant teeth will be identified and recorded for assessment using the Calcivis System as per Inclusion / Exclusion criteria.

All teeth surfaces to be imaged will be cleaned by the Dentist, by brushing with water or dental paste and rinsing with water and an air-water spray from a conventional dental 3-in-1 device, according to the Tooth Cleaning Protocol (Appendix 2 of the Clinical Study Plan). Patients will be asked to rinse out thoroughly with tap water.

Immediately following thorough air-drying of each tooth surface to be imaged, the Investigator will take a colour photograph with a standard intra-oral camera and record the ICDAS score /activity status.

#### Preparation Procedures for imaging with the Calcivis device

Care must be taken to ensure the surface of the tooth and surrounding area are free from saliva before imaging by the use of appropriate moisture control aids.

Each tooth will be air-dried for 5 to 10 seconds immediately before application of the disclosing solution and Calcivis System imaging.

#### Imaging with the Calcivis System

For teeth from each category (no lesions, and active lesions) a maximum of one tooth per patient can be imaged.

If a patient has more than one tooth of a particular category (sound tooth [no visible lesion], or tooth with active lesion) the investigator will use best clinical judgement to choose a tooth that most clearly fits the criteria of that particular population tooth type, for example if there is the choice of 2 teeth displaying lesions considered active, each identical except one of the teeth has a lesion in a plaque stagnation area (e.g. pits and fissures) and one more distant from plaque stagnation area, the tooth with the lesion in a plaque stagnation area will be chosen.

If the first image of a selected tooth is not clear for interpretation, it is acceptable to take a second image of that tooth, however no more than two images of any one tooth can be taken.

Recruitment will be stopped for each Investigator when a minimum of 17 evaluable images (as determined by the Investigators) from each tooth population have been obtained.

After all imaging has been completed, patients will be asked to rinse out with tap water.

Any adverse events observed or volunteered by the patient will be recorded. If appropriate a colour photograph will be taken of the adverse event with a standard intra-oral camera.

The images generated with the Calcivis System will be stored digitally on the laptop provided. The software will allow overlay of the two sets of images (before and after application of the disclosing solution) and interpretation of the resulting demineralization map of each imaged tooth will be carried out by the Investigator at the end of imaging.

At the end of the imaging procedures, the Investigator will share the images of the teeth with the patient.

The Calcivis System will be dismantled and cleaned according to the Instructions for Use. All consumables will be disposed according to the Instructions for Use.

Representatives of the Sponsor, Calcivis Ltd, will be available throughout Visit 1 to provide technical support for the use of the Calcivis System, as and when required. Consent will be sought from the patient and / or parent or guardian.

#### Post-Imaging Questionnaires / Visual Analogue Scales

At the end of the imaging procedures, patients will be asked to remain at the dental practice to complete a Patient Questionnaire / Visual Analogue Scale. Visit 1 is then complete.

In addition, at the end of each imaging study visit, the Investigator and Dental Nurse will each complete relevant sections of a User Questionnaire.

### **5.3 Study Visit 2 – 7-14 days post-imaging**

At this visit, a final oral examination will be performed by the Investigator and any adverse events observed or volunteered by the patient will be recorded. If appropriate, a colour photograph will be taken of the adverse event with a standard intra-oral camera.

## 5.4 Future Dental Care

Depending on the results, the Investigator may provide caries preventive advice to the patient and / or parent or guardian. The Investigator will not suggest further dental treatment based on the result of the images alone.

## 5.5 Independent Investigator Image Review

After all the images have been taken and verified as acceptable by the originating Investigator, and the CRFs collected, an independent review of the Calcivis images will be undertaken to assess the presence or absence of elevated luminescence on the surface to the teeth imaged with the Calcivis System.

This will be carried out by one of the other Investigators.

The independent reviewer will be provided with evidence of both the original investigator's decision on tooth classification (i.e. no lesion, or active lesion, based on ICDAS coding / activity status) along with documented evidence of the clinician's intended location for assessment (this is all documented by the original Investigator prior to imaging using the Calcivis System). In addition, photographic evidence of the actual location of the luminescence will be provided. The determination by the independent reviewer will be made off-site, using the visible and Calcivis images along with copies of the original Investigator's documentation. The data from the independent reviewer will be used for the primary analysis.

## 6.0 Sample Size

The study will assess the agreement between the Calcivis System and dentist rating of suitable teeth in two teeth populations: 'no visible lesions', and 'active lesions'. Based on previous study data and expert opinion, 'No visible lesions' are expected to correspond to 'no luminescence' according to the Calcivis system in at least 70% of cases. Similarly, 'active lesions' are also expected to correspond to 'luminescence' in at least 70% of cases.

Subjects will provide no more than one tooth of each tooth population. The study sample size is calculated in terms of the number of teeth of each tooth population required. The number of subjects required is then *at most* the total number of teeth required.

For the purpose of sample size calculations, the percentage agreement for each of the two tooth populations are jointly considered as measures of agreement. That is, the study will be deemed a success if the percentage agreement in both of the tooth status populations is statistically significant at the 2.5% level when compared to chance agreement (50%).

Expressed in terms of hypothesis tests, the null and alternative hypotheses are:

$H_0: pa,i=0.5$  vs.  $H_1: pa,i>0.5$  for each tooth status population  $i$

where  $pa,i$  is the percentage agreement in tooth status population  $i$ .

To achieve at least 90% power overall, a power of 94.9% has been used for each tooth status population individually. The planned method of analysis is an exact binomial test

and this has been used to derive a required sample size of 81 for each of the tooth status populations. This is the first sample size after which all subsequent sample sizes provide at least 94.9% power.

## **7.0 Deviations**

A Deviation is a failure to comply with the requirements specified within the Clinical Study Plan without adequate justification.

All deviations will be documented on the appropriate forms and reported to the Sponsor. All deviations will be reviewed and assessed for their impact on patient safety and validity for analysis by Calcivis Ltd.

## **8.0 Analysis Populations**

### ***8.1 Safety Population***

All patients on whom the Calcivis System is used will be included in the Safety Population.

### ***8.2 Agreement Population***

The Agreement Population will include all teeth on which there is a dentist ICDAS score. The Agreement Population will be used for all analyses of agreement.

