7.4 Inclusion and Exclusion criteria

Inclusion criteria

1. Patient must be \geq 6 years old
2. Patient must have one unrestored, accessible, free smooth buccal surface on a canine or incisor, away from the gingival surface identified with no visible lesion (coded ICDAS 0) – ref. table below
and / or
3. Patient must have one unrestored, accessible, erupting or erupted molar or pre-molar with a visible lesion identified (coded ICDAS 2 or 3) in a plaque stagnation area – ref. table below
4. Patient and / or parent or guardian must be willing and able to give written informed consent
5. Patient and / or parent or guardian must be willing and able to adhere to study schedule

Tooth status population	Exemplar tooth type and location	Additional criteria
Sound tooth	Canine or incisor Away from gingival margin	Enamel should be shiny and feels hard and smooth when the tip of a probe is moved gently across the surface
Active Lesion	Erupting or erupted Molars Fissure pits of occlusal surface	Surface of enamel should be whitish/yellowish opaque with loss of luster; feels rough when the tip of a probe is moved gently across the surface. Lesion should be in a plaque stagnation area i.e. pits and fissures; approximately, near the gingival surface below the contact point.
Inactive Lesion	Molars and pre-molars Smooth surface away from gingival margin	Surface of enamel should be whitish, brownish or black. Enamel should be shiny and feels hard and smooth when the tip of a probe is moved gently across the surface. For smooth surfaces, the caries lesion will be typically located at some distance from the gingival margin.

Exclusion criteria

1. Any Patient with recent tooth bleaching (within previous two weeks of imaging with the Calcivis System)
2. Any Patient having on-going re-mineralization treatment including, but not limited to high concentration prescription fluoride toothpaste
3. Any patient with a fixed orthodontic appliance
4. Any patient currently taking part in a clinical research study, or has taken part in a clinical research study in the previous three months
5. Pregnant and / or nursing mothers

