All teeth surfaces to be imaged will be cleaned by the Dentist, by brushing with water or dental paste and rinsing with water and an air-water spray from a conventional dental 3-in-1 device, according to the Tooth Cleaning Protocol (Appendix 2). Patients will be asked to rinse out thoroughly with tap water.

Immediately following thorough air-drying of each tooth surface to be imaged, the Investigator will take a colour photograph with a standard intra-oral camera and record the ICDAS score /activity status.

Preparation Procedures for imaging with the Calcivis device

Care must be taken to ensure the surface of the tooth and surrounding area are free from saliva before imaging by the use of appropriate moisture control aids.

Each tooth will be air-dried for 5 to 10 seconds immediately before application of the disclosing solution and Calcivis System imaging.

Imaging with the Calcivis System

For teeth from each category (no lesions, and active lesions) a maximum of one tooth per patient can be imaged.

If a patient has more than one tooth of a particular category (sound tooth [no visible lesion], or tooth with active lesion) the investigator will use best clinical judgement to choose a tooth that most clearly fits the criteria of that particular population tooth type, for example if there is the choice of 2 teeth displaying lesions considered active, each identical except one of the teeth has a lesion in a plaque stagnation area (e.g. pits and fissures) and one more distant from plaque stagnation area, the tooth with the lesion in a plaque stagnation area will be chosen.

If the first image of a selected tooth is not clear for interpretation, it is acceptable to take a second image of that tooth, however no more than two images of any one tooth can be taken.

Recruitment will be stopped for each Investigator when a minimum of 17 evaluable images (as determined by the Investigators) from each tooth population have been obtained.

After all imaging has been completed, patients will be asked to rinse out with tap water.

Any adverse events observed or volunteered by the patient will be recorded. If appropriate a colour photograph will be taken of the adverse event with a standard intra-oral camera.

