8.5 Independent Investigator Image Review

After all the images have been taken and verified as acceptable by the originating Investigator, and the CRFs collected, an independent review of the Calcivis images will be undertaken to assess the presence or absence of elevated luminescence on the surface to the teeth imaged with the Calcivis System.

This will be carried out by one of the other Investigators as follows:

Site	Original Investigator	Independent Investigator
1	[name]	[name]
1	[name]	[name]
3	[name]	[name]
3	[name]	[name]
5	[name]	[name]

The independent reviewer will be provided with evidence of both the original investigator's decision on tooth classification (i.e. no lesion, or active lesion, based on ICDAS coding / activity status) along with documented evidence of the clinician's intended location for assessment (this is all documented by the original Investigator prior to imaging using the Calcivis System). In addition, photographic evidence of the actual location of the luminescence will be provided. The determination by the independent reviewer will be made off-site, using the visible and Calcivis images along with copies of the original Investigator's documentation. The data from the independent reviewer will be used for the Primary analysis.

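### Does the Active lesion row of the agreement analysis need a written rule for ICDAS 2 or 3 teeth recorded as inactive?

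*SAP*

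**What the plan says.** - **Entry (Protocol 7.4, criterion 3).** The lesion must lie where plaque collects, and the tooth is admitted by code: "Patient must have one unrestored, accessible, erupting or erupted molar or pre-molar with a visible lesion identified (coded ICDAS 2 or 3"). Activity is not mentioned. The table it refers to describes three tooth statuses: sound, active lesion and inactive lesion. The inactive row includes "Surface of enamel should be whitish, brownish or black".
- **Imaging (Protocol 8.2).** "For teeth from each category (no lesions, and active lesions) a maximum of one tooth per patient can be imaged". Before imaging, the investigator photographs the surface and must "record the ICDAS score /activity status".
- **Independent review (Protocol 8.5).** The reviewer receives the original investigator's "decision on tooth classification (i.e. no lesion, or active lesion, based on ICDAS coding / activity status"), and "this is all documented by the original Investigator prior to imaging using the Calcivis System".
- **Population (SAP 8.2; same rule in Protocol 10.2).** "The Agreement Population will include all teeth on which there is a dentist ICDAS score".
- **Analysis.** Protocol 10.2 tests teeth rated as having an active lesion. SAP 11 describes the dentist's status as ICDAS-defined and gives it two levels, no visible lesion and active lesion. Table 5 splits by code (0, 2, 3). Table 6, which holds the tests, has a No visible lesion row and an Active lesion row.
- **Deviations (SAP 7.0).** The sponsor assesses every deviation for its effect on patient safety and on validity for analysis.

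**The concern.** The codes in Protocol Appendix 1 grade the extent of a lesion and say nothing about activity. Entry and the Agreement Population follow code or score, while the tested row is named by activity. No sentence maps code plus recorded activity to a row of Table 6. An ICDAS 2 or 3 tooth recorded inactive could then be handled in two ways. Read by code, it joins the Active lesion row and, if dark, counts as a disagreement. Read by activity, it drops out.

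Both tests must succeed for the study to succeed, so the choice could change N, the percentage and the p-value of a deciding test, and it could be made after the results are known. The count of 17 evaluable images per Investigator depends on the same definition.

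The Protocol 5.7 account of the earlier study adds to the worry. It describes the same 34 lesion teeth both as visible lesions and as lesions judged active, while expecting only about 55% of lesions to be active.

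**Working it through.** **1. The plan's own figure.** Inputs from Protocol 10.1 and SAP 6.0: exact binomial test, null 0.50, alternative 0.70, one-sided 2.5%, 94.9% power per population (√0.90 = 0.9487). At n = 81 the smallest passing count is 50, because P(X ≥ 50 | 0.5) = 0.0224. Power is P(X ≥ 50 | 0.7) = 0.957, and jointly 0.957² = 0.916. The stated 81 reproduces against the unrounded target, so the sample size is not in question.

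**2. Which reading the texts support.**

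| Text | Points to |
|---|---|
| Protocol synopsis, Statistical Rationale: dentist rates teeth into two categories, no visible lesion or active lesion | Activity |
| Protocol 8.2: only these two categories are imaged | Activity |
| Protocol 8.5: tooth is classified as no lesion or active lesion, from code and activity status | Activity |
| Protocol 10.2: teeth rated as having an active lesion | Activity |
| SAP 10.1 and Table 1 footnote: Agreement Population subjects have a tooth with no visible lesion, one with an active lesion, or both | Activity |
| SAP Listings 3 and 11: template values allow no visible-but-inactive lesion | Activity |
| SAP 11: status called ICDAS-defined, but glossed with the same two levels | Either |
| SAP Table 5: rows by code; descriptive, not the test | Code |

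The population sentence in SAP 8.2 is the short form. The outputs built on it leave no place for an inactive-lesion tooth.

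**3. When the readings part.** Let n be the ICDAS 2 or 3 teeth analysed and m those recorded inactive. By activity, the test uses the lit teeth among n − m. By code, it uses the lit teeth among n. With m = 0 the two are identical.

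**4. How often the decision differs.** Lit active teeth are Bin(n − m, 0.70) and lit inactive teeth are Bin(m, q). The documents give neither m nor q, so both are assumed. I take q = 0.16 (5 of 31 sound teeth lit in the earlier study, Protocol 5.7), 0.30 (1 − 0.70) and 0.50. Planned n is 85 to 90.

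For n = 85 and m = 1 the passing counts are 52/84 and 53/85. The readings disagree only if exactly 52 active teeth are lit and the stray is dark: P(X = 52; 84, 0.7) × (1 − q) = 0.0255 × 0.839, 0.70 or 0.50, which gives 2.1%, 1.8% or 1.3%.

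For n = 90 and m = 1 the passing count is 55 for both 89 and 90 teeth. They disagree only if exactly 54 active teeth are lit and the stray is lit: 0.015 × q = 0.2%, 0.45% or 0.75%.

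Summing the general case, with entries for q = 0.16 / 0.30 / 0.50:

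| m | n = 85 | n = 90 |
|---|---|---|
| 0 | 0 | 0 |
| 1 | 2.1 / 1.8 / 1.3% | 0.2 / 0.45 / 0.75% |
| 2 | 4.5 / 3.6 / 2.5% | 1.4 / 1.1 / 0.8% |
| 4 | 8 / 6 / 3% | 4 / 2 / 1% |
| 9 | 22 / 13 / 5% | 15 / 9 / 3% |
| 17 | 61 / 39 / 13% | 48 / 27 / 7% |

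**5. Reading the lower rows.** Nine of 85 is 10.6% and 17 of 85 is 20% of lesion teeth imaged against Protocol 8.2. A striking example is 52/76 = 68.4% (p = 0.0009, pass) against 52/85 = 61.2% (p = 0.0251, fail; 53 needed). It requires all nine inactive teeth to be dark, which has probability 0.839⁹ = 0.21 at q = 0.16 and 0.70⁹ = 0.04 at q = 0.30.

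**6. Likely m.** The eruption table in Protocol 5.7 gives inactive shares from 9/193 = 5% to 164/212 = 77%. Those are shares of all non-cavitated lesions in a published series. They are not the share left after an investigator has chosen a tooth because its lesion looks active.

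**The case for a change.** The strongest case for a change is that Protocol 8.2 governs conduct and is not an analysis rule. If an inactive lesion is imaged, SAP 7.0 leaves its handling to the sponsor without a criterion, on the denominator of a deciding test. The choice also has a direction. At n = 85 with nine such teeth, essentially all the discordance is a pass by activity and a fail by code (0.220 of 0.220 at q = 0.16; 0.131 of 0.132 at q = 0.30), so the natural reading is usually the one that favours the device. A defining sentence before database lock would cost almost nothing.

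Some of this stands. The SAP has no such sentence, and its SAP 11 label and Table 5 leave room for a reading by code. The direction is also right in most scenarios, although with a single stray at n = 90 it reverses.

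It does not stand that the outcome is open to quiet choice. Classification is documented before imaging. Listing 9 prints the ICDAS code beside an inactive-or-active column, Listing 11 prints the independent luminescence finding, and deviations have their own table and listing. A reader can identify any ICDAS 2 or 3 tooth recorded inactive and rerun the test either way. The loose wording about the earlier study concerns different eligibility (ages 16 to 25, ICDAS 1 to 3) and does not show how this SAP will be programmed.

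The absence of a tested inactive-lesion group limits what success can show, but no row definition would cure that, and Protocol 5.6 already presents the device as an aid and not as diagnostic in itself.

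**Conclusion.** No change follows. The gap is one of wording: no stated rule gives a wrong result, and the two readings coincide whenever Protocol 8.2 is followed. The protocol's analysis text and most SAP outputs already point to a row defined by recorded activity, which is how an analyst would most likely build it. A stray tooth would be a deviation, listed and reviewed for validity for analysis.

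With one or two strays the chance of opposite decisions is 1.3% to 4.5% at n = 85 and 0.2% to 1.4% at n = 90. This rests on 70% luminescence in active lesions, an assumed 16% to 50% in inactive ones, and few departures from Protocol 8.2. If nine or more of the lesion teeth were recorded inactive the figure would be material (up to 22% at n = 85 with nine), but nothing in the documents suggests departures on that scale, and the listings would show them.

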## **9.0 Data Reporting Conventions**

### ***9.1 Descriptive Statistics***

Unless otherwise stated, all continuous parameters will be summarized using standard summary statistics as appropriate (n, mean, standard deviation, minimum, median and maximum). Summary statistics for categorical variables will include frequency counts and percentages.

In the presentation of descriptive summary statistics, the minimum and maximum will be presented to the same number of decimal places as the variable being reported. If differing levels of precision are recorded then the most frequently recorded precision will be used as the basis for reporting precision. In the event of a tie, the higher level of precision will be used for summarising data. The mean and median will be reported to one extra decimal place; the standard deviation (SD) to two extra decimal places.

Frequency counts will be provided for categorical variables (e.g., gender). Unless otherwise stated, this will consist of the number of patients in a particular category and the percentage of the total number of patients, presented to one decimal place.

Analyses will be performed using the validated statistical software Statistical Analysis System (SAS) version 9.2 (or higher).

